
 
● Panel A: 
 
○ Day 1 and Day 4: predose, 2, 6, 8, 10, 12, 16 and 24 hours postdose
 
○ Day 7: predose, 2, 6, 8, 10, 12, 16, 24, 36 and 48 hours postdose
 
 
 
● Panel B: 
 
○ Day1: predose, 2, 6, 8, 10, 12 and 16 hours postdose
 
○ Day 2 and Day 3: predose, 2, 6 and 8 hours postdose
 
○ Day 7: predose, 2, 6, 8, 10, 12, 16, 24, 36 and 48 hours postdose
 
 
 
● Panel C: 
 
○ Day 1 and Day 2: predose, 2, 6, 8, 10, 12 and 16 hours postdose
 
○ Day 3: predose, 2, 6, 8, 10, 12, 16 and 24 hours postdose
 
○ Day 7: predose, 2, 6, 8, 10, 12, 16, 24, 36 and 48 hours postdose
 
 
 
● Optional sample when signs of dystonia and/or akathisia occur.
 
● Leftover main study plasma will be stored for future biomedical research if the participant consents to future biomedical research.
 
															
k. This sample will be drawn for CYP2C9 and for planned analysis of the association between genetic variants in DNA and drug response. If the IRB/IEC does not approve of the planned analysis of the association between DNA variation and drug response, or if there is a local law or regulation prohibiting the same, data analysis will be limited to CYP2C9. Leftover extracted DNA will be stored for future biomedical research.															

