  - Day 1, Day 4, Day 7 and Day 13: 8, 16 and 24 hours postdose
  - Day 15: Time-matched to 24-hour postdose vital signs.
- d. Orthostatic assessments in HR and BP will follow semi-recumbent vital sign assessments. Participants should be standing for approximately 2 minutes prior to the orthostatic assessments. Orthostatic HR and BP measurements will be obtained on:
  - Day -1: Time-matched to 8, 16 and 24 hours postdose orthostatic vital signs
  - Day 1, Day 4, Day 7 and Day 13: 8, 16 and 24 hours postdose

Scheduled Day	Screening	Washout	Intervention														Poststudy	Notes		
			-6	-2	-1	1	2	3	4	5	6	7	8	9	10	11	12	13	14	15

- Day 15: Time-matched to 24-hour postdose orthostatic vital signs

e. Scheduled assessments are completed predose on dosing days and at any time on non-dosing days.

f. Single 12-lead safety ECG measurements will be taken at all postdose timepoints. On the following days, specific timepoints are noted:

- Day 1: Triplicate measurements within 2 hours prior to dosing
- Day 1, Day 4, Day 7 and Day 13: 8, 16 and 24 hours post-dose

g. Screening UDS is mandatory; any additional UDS are conducted per site SOP. UDS prior to randomization will be done on the day of admission.

h. Additional BARS, AIMS and SAS assessments will be conducted as soon as possible when there are observed or reported complaints of dystonia and/or akathisia (See Section 8.3.6).

i. MK-8189 plasma PK sample collection:

- Day 1, Day 4, and Day 7: predose, 2, 6, 8, 10, 12, 16 and 24 hours postdose.
- Day 13: predose, 2, 6, 8, 10, 12, 16, 24, 36 and 48 hours postdose
- Optional sample when signs of dystonia and/or akathisia occur.
- Leftover main study plasma will be stored for future biomedical research if the participant consents to future biomedical research.

j. This sample will be drawn for CYP2C9 and for planned analysis of the association between genetic variants in DNA and drug response. If the IRB/IEC does not approve of the planned analysis of the association between DNA variation and drug response, or if there is a local law or regulation prohibiting the same, data analysis will be limited to CYP2C9. Leftover extracted DNA will be stored for future biomedical research.

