b. Participants will be confined minimally from Day -6 until Day 11 procedures are complete.

c. Single HR and BP measurements will be obtained at all timepoints unless otherwise noted. On the following days, specific timepoints are noted:

- Day -1 (triplicate measurements): Time-matched to 8, 16 and 24 hours postdose vital signs.
- Day 1, Day 2, Day 3 and Day 9: 8, 16 and 24 hours postdose
- Day 11: Time-matched to 24-hour postdose vital signs

d. Orthostatic assessments in HR and BP will follow semi-recumbent vital sign assessments. Participants should be standing for approximately 2 minutes prior to the orthostatic assessments. Orthostatic HR and BP measurements will be obtained on:

- Day -1: Time-matched to 8, 16 and 24 hours postdose orthostatic vital signs.
- Day 1, Day 2, Day 3 and Day 9: 8, 16 and 24 hours postdose
- Day 11: Time-matched to 24-hour postdose orthostatic vital signs

e. Scheduled assessments are completed predose on dosing days and at any time on non-dosing days.

f. Single 12-lead safety ECG measurements will be taken at all postdose timepoints. On the following days, specific timepoints are noted:

- Day 1: Triplicate measurements within 2 hours prior to dosing
- Day 1, Day 2, Day 3 and Day 9: 8, 16 and 24 hours post-dose

g. Screening UDS is mandatory; any additional UDS are conducted per site SOP. UDS prior to randomization will be done on the day of admission.

h. Additional BARS, AIMS and SAS assessments will be conducted as soon as possible when there are observed or reported complaints of dystonia and/or akathisia (See Section 8.3.6).

i. MK-8189 plasma PK sample collection:

- Day 1 and Day 2: predose, 2, 6, 8, 10, 12 and 16 hours postdose
- Day 3: predose, 2, 6, 8, 10, 12, 16 and 24 hours postdose
- Day 9: predose, 2, 6, 8, 10, 12, 16, 24, 36 and 48 hours postdose
- Optional sample when signs of dystonia and/or akathisia occur.
- Leftover main study plasma will be stored for future biomedical research if the participant consents to future biomedical research.

j. This sample will be drawn for CYP2C9 and for planned analysis of the association between genetic variants in DNA and drug response. If the IRB/IEC does not approve of the planned analysis of the association between DNA variation and drug response, or if there is a local law or regulation prohibiting the same, data analysis will be limited to CYP2C9. Leftover extracted DNA will be stored for future biomedical research.

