## 4 STUDY DESIGN

### 4.1 Overall Design

This is a 2-part randomized, placebo-controlled, parallel-group, double-blind study of MK-8189 in participants with schizophrenia and healthy participants. Part 1 will enroll young adult participants with schizophrenia and Part 2 will enroll healthy elderly participants and elderly participants with schizophrenia.

#### Part 1

In all panels, participants will be washed off their current antipsychotic therapy. The washout may start with a down titration of the antipsychotic treatment during the screening phase per direction of the investigator. Participants should not receive antipsychotics for at least 5 days or 3 half-lives (whichever is longer) prior to Day -1. For longer half-life antipsychotics (e.g. aripiprazole and brexpiprazole), if deemed appropriate by the investigator, a participant may stop treatment (i.e. cessation of AAP) as an outpatient, but should be confined to the clinical research unit within a week of stopping treatment and minimally beginning on Day -6.

Decisions regarding the initiation of an alternate titration regimen will be made jointly between the principal investigator(s) and Sponsor and will be based on safety and tolerability from ~ 8 subjects as further detailed later in this section.

Panel A will enroll up to 16 participants with schizophrenia disorder who will receive Titration Regimen 1. An initial cohort of 8 participants will be randomized to active or placebo. Beginning on Day 1, participants randomized to MK-8189 will receive 16 mg (1 x 12-mg tablet and 1 x 4-mg tablet) of MK-8189 on Days 1 to 3 and 24 mg of MK-8189 (2 x 12-mg tablets) on Days 4 to 7. Participants randomized to placebo will receive the same number of tablets matching the MK-8189 tablet strengths in the active group.

After dosing of the initial cohort of 8 participants completes in Panel A, Panel B or Panel C will be enrolled. If safety and tolerability data from Panel A indicate a starting dose of MK-8189 16 mg is generally well tolerated, Panel B will be enrolled. If a starting dose of MK-8189 16 mg is not generally well tolerated, Panel C will be enrolled.

Panel B will enroll an initial cohort of 8 participants with schizophrenia disorder who will receive Titration Regimen 2. Participants will be randomized to MK-8189 or placebo. On Days 1 to 7, participants will receive MK-8189 24 mg (2 x 12-mg tablets) or matched placebo.

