Panel D will run concurrently with Part 1. Panel D will enroll up to 16 participants with schizophrenia disorder. An initial cohort of 8 participants will be randomized to active or placebo. Beginning on Day 1, participants randomized will begin to receive MK-8189/placebo QD and will be titrated from 8 mg to 24 mg or placebo over the course of a 13-day treatment period as follows: 8 mg (2 x 4 mg/placebo tablets) Days 1 to 3, 16 mg (1 x 12 mg/placebo tablet and 1 x 4 mg/placebo tablet) Days 4 to 6, 24 mg (2 x 12 mg/placebo tablets) Days 7 to 13. This titration schedule has been shown to be well tolerated in a previous trial (P007) in young adults with schizophrenia.

Each dose titration decision for each individual participant will occur after 3 days of dosing per dose level. If a participant does not tolerate escalation to the next dose, the participant may be titrated down to the previous dose. If appropriate medical care necessitates a down-dose, the investigator may do so independent of consultation with the Sponsor. If the participant tolerates continued dosing following down-titration, the participant may continue in the trial at that dose until study completion or may be rechallenged at a higher dose. During the titration period, rechallenges are only to occur on a regularly scheduled dose titration day, ie, Day 7, and will not extend the participant's time in the study. Any changes to the protocol specified titration schedule (eg, the participant remains at their current dose or is down titrated) will be documented in a protocol clarification letter.

Participants will be confined to the unit from Day -6 until the Day 15 postdose assessments are complete.

[figure not shown]
After dosing of the initial cohort of approximately 8 participants, if the dose regimen is found to be generally well tolerated, Panel E will be enrolled. If additional data are required for evaluation, additional participants (up to 8) may be enrolled. The decision to enroll additional participants in Panel D or initiate Panel E will be made jointly between the investigator(s) and the Sponsor and documented in a protocol clarification letter.

Panel E will be initiated after completion of Part 1 and dosing of at least 8 participants in Panel D. If dosing in Panel D is generally well tolerated and at least 1 of the titration regimens evaluated in Part 1 of the current protocol is found to be generally well tolerated, 1 of those 3 regimens will be administered in Panel E.

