**Pharmacokinetics:**

Separately for each part and each PK parameter, individual values of AUC0-24hr, Cmax, and C24hr at each dose level will be natural log-transformed and evaluated with a linear mixed effects model containing a fixed effect for dose and a random effect for subject. For each PK parameter, GM and corresponding ninety-five percent Cis for each dose will be provided.

The comparison of elderly participants with schizophrenia to young adults with schizophrenia will be made using data from Part 2 and Part 1, and historical data from P007 (Panel B and D). Separately for each PK parameter individual values of AUC0-24hr, Cmax, and C24hr at each dose level (16 mg and 24 mg at steady state) will be natural log-transformed and evaluated with a linear mixed effects model containing fixed effects for dose, population (elderly, adult), and population by dose interaction and a random effect for subject. For each population, GMs and corresponding 95% CIs for each dose will be provided. Similarly, the comparison of healthy elderly participants (Panels F and G) to healthy young adults (Panel A in P007) will be made using the above described model.

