### Comparison of Elderly Participants and Young Adults

The comparison of elderly participants with schizophrenia to young adults with schizophrenia will be made using data from Part 2 (Panels D and E) and Part 1, and historical data from P007 (Panels B and D). Separately for each PK parameter, individual values of AUC0-24hr, Cmax, and C24hr at each dose level (16 mg and 24 mg at steady state) will be natural log-transformed and evaluated with a linear mixed effects model containing fixed effects for dose, population (elderly, adult), and population by dose interaction and a random effect for subject. Kenward and Roger's method will be used to calculate the denominator degrees of freedom for the fixed effects. For each population, 95% CIs for the least squares means for each dose will be constructed on the natural log scale. Exponentiating the least-squares means, and lower and upper limits of these CIs will yield estimates for the population GMs and CIs about the GMs on the original scale. Individual PK values, GMs and 95% CIs will be shown graphically by population. A two-sided 90% CIs for the true differences in mean for log-transformed AUC0-24hr, Cmax, and C24hr (elderly – adults) will also be computed from the model. These CIs will be exponentiated to obtain the 90% CIs for the AUC0-24hr, Cmax, and C24hr true geometric mean ratios (elderly/adults). Additionally, a plot of GMR with corresponding 90% CI will also be provided.

Similarly, the comparison of healthy elderly participants (Panels F and G) to healthy young adults (Panel A in P007) will be made using the above described model.

The exploratory objective pertaining to the assessment of relationship between CYP2C9 genetic polymorphs and the laboratory, and PK of MK-8189, and the relationship between genetic variation and response to the treatment may be addressed in a separate report.

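### The elderly versus young-adult comparison at 16 mg steady state has no steady-state 16-mg AUC or Cmax behind it: every 16-mg profile is taken on the first 16-mg day

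*Combined protocol and SAP*

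**What the plan says.** Section 9.1 plans the age comparison on "individual values of AUC0-24hr, Cmax, and C24hr at each dose level (16 mg and 24 mg at steady state". Section 9.6 repeats this: values "at each dose level (16 mg and 24 mg at steady state) will be natural log-transformed" and enter a mixed model with dose, population, their interaction and a random subject effect. Geometric mean ratios (elderly/adults) with 90% CIs are reported and plotted.

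The schizophrenia comparison sets Panels D and E against Part 1 pooled with P007 Panels B and D. The other is "the comparison of healthy elderly participants (Panels F and G) to healthy young adults (Panel A in P007", with the same model.

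The sampling footnotes and dosing days are these:

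- Panels D/F (Section 1.3.2): "Day 1, Day 4, and Day 7: predose, 2, 6, 8, 10, 12, 16 and 24 hours postdose", plus Day 13. Section 4.1 gives "16 mg (1 x 12 mg/placebo tablet and 1 x 4 mg/placebo tablet) Days 4 to 6".
- Part 1 Panel A (Section 1.3.1): "Day 1 and Day 4: predose, 2, 6, 8, 10, 12, 16 and 24 hours postdose", plus Day 7. Section 4.1 gives "16 mg (1 x 12-mg tablet and 1 x 4-mg tablet) of MK-8189 on Days 1 to 3". Panel E/G Titration Regimen 1 (Section 1.3.3) has the same first two profile days, plus Day 10.
- Panel E/G Titration Regimen 3 (Section 1.3.5): "Day 1 and Day 2: predose, 2, 6, 8, 10, 12 and 16 hours postdose", then Days 3 and 9. Day 2 is its only 16-mg day. Part 1 Panel C has the same pattern, ending on Day 7.
- Part 1 Panel B and Regimen 2 give no 16 mg.

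Neither section names the day that supplies the 16-mg value, in this study or in P007.

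**The concern.** The model needs a 16-mg steady-state value for each population. For AUC0-24hr and Cmax the schedule provides none, so read literally those cells are empty. In practice the analyst would probably use whatever 16-mg profile exists. The 16-mg ratio would then compare people at different stages of accumulation: after three days of 8 mg, after one day of 8 mg, after no drug at all, or (P007 Panels A and B) after three days of 12 mg.

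The model has no term for day, panel or study, so that difference would go into the population effect at 16 mg and into the population-by-dose interaction. In the healthy comparison the pull is always downward, which could mask a real rise in elderly exposure. In the schizophrenia comparison the direction depends on the panel mix.

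**Working it through.** **1. Is a later 16-mg profile scheduled anywhere?** Setting dosing days against profile days:

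| Panel | 16-mg days | Profile days | 16-mg profile |
|---|---|---|---|
| D/F | 4–6 | 1, 4, 7, 13 | Day 4, straight after 8 mg |
| Part 1 A | 1–3 | 1, 4, 7 | Day 1, first dose ever |
| E/G Regimen 1 | 1–3 | 1, 4, 10 | Day 1, first dose ever |
| Part 1 C | 2 | 1, 2, 3, 7 | Day 2, only 16-mg dose |
| E/G Regimen 3 | 2 | 1, 2, 3, 9 | Day 2, only 16-mg dose |
| Part 1 B, E/G Regimen 2 | none | 1, 2, 3, 7 | none |

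Appendix 8 sample counts agree with the footnotes: D/F 8+8+8+10 = 34, Regimen 1 8+8+10 = 26, Regimen 2 7+4+4+10 = 25. Regimen 3 and Panel C count 7+7+8+10 = 32 against 34 in Appendix 8, but they have only one 16-mg day. No later 16-mg profile is hidden.

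The one sample near 16-mg steady state is the predose sample on the first 24-mg day, after the third 16-mg dose (Day 7 in D/F, Day 4 in Panel A and Regimen 1). It gives C24hr only.

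**2. How far from steady state is the first day?** Section 2.2.2 gives a half-life of about 8.4 h, so k = ln 2/8.4 = 0.0825 per hour. It gives median Tmax of 10–20 h. The absorption shape is not given, so I assumed five: bolus, first-order with Tmax 10 h, and zero-order input over 10, 12 or 20 h.

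Let F_n be the share of a single dose's total AUC that falls in its first n days. With linear kinetics, AUC as a share of 16-mg steady state is:

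- Panel A and Regimen 1, Day 1: F_1
- D/F, Day 4: F_1 + 0.5(F_4 − F_1)
- Panel C and Regimen 3, Day 2: F_1 + 0.5(F_2 − F_1)

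Bolus: F_n = 1 − exp(−24nk), so F_1 = 0.862, F_2 = 0.981, F_4 ≈ 1. The shares are 0.86, 0.93 and 0.92.

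Zero-order over 20 h: F_n = 1 − exp(−24nk)(exp(20k) − 1)/(20k), so F_1 = 0.648, F_2 = 0.951, F_4 ≈ 0.999. The shares are 0.65, 0.82 and 0.80.

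Over all five shapes, with Cmax read at the protocol sampling times:

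| First 16-mg day | AUC share | Cmax share |
|---|---|---|
| D/F Day 4 | 0.82–0.93 | 0.85–0.93 |
| Panel A, Regimen 1 Day 1 | 0.65–0.86 | 0.71–0.86 |
| Panel C, Regimen 3 Day 2 | 0.80–0.92 | 0.82–0.92 |

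Across half-lives of 6–12 h the AUC shares are 0.76–0.97, 0.53–0.94 and 0.71–0.97. The last-day 24-mg profile in every panel is at least 0.99 of steady state. So is C24hr after the third 16-mg dose at 8.4 h (0.98 at 12 h).

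**3. Expected 16-mg AUC ratio with no age effect.** P007 sampling days are not in the documents, so both cases are shown. P007 Panels A and B gave 16 mg on Days 10–12 after 12 mg. P007 Panel D is assumed to step from 8 to 16 mg after 3 days.

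| Comparison | P007 on third 16-mg day | P007 on first 16-mg day |
|---|---|---|
| Panel F v P007 A | 0.83–0.93 | 0.90–0.96 |
| Panel G Regimen 1 v P007 A | 0.65–0.86 | 0.71–0.89 |
| Panel G Regimen 3 v P007 A | 0.80–0.92 | 0.88–0.95 |
| Panel D v P007 D | 0.83–0.93 | 1.00 |

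Within this study, Panel D Day 4 against Panel A Day 1 gives 1.08–1.27 (Cmax 1.08–1.20). Against Panel C Day 2 it gives 1.01–1.03. Panel E Regimen 1 against Panel A gives 1.00.

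Pooling the young adults as Section 9.6 plans (12 active in P007 B, 17 in P007 D, 6 or 12 assumed in Panel A, equal weights, Panel D alone as the elderly group) gives 1.00–1.04 (first day) or 0.89–0.97 (third day).

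**4. Scale.** Table 4 half-widths reproduce as t(0.95, n1+n2−2) × SD × √(1/n1 + 1/n2): 1.717 × 0.38 × √(2/12) = 0.266, and 1.725 × 0.60 × √(1/10 + 1/12) = 0.443. On the log scale:

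- The pooled schizophrenia bias is at most |ln 0.89| = 0.12, under half of 0.266. The pairwise 1.27 is 0.24.
- In the healthy comparison, Panel F at 0.83 is 0.19 and Panel G on Regimen 1 at 0.65 is 0.43, against 0.443.

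**The case against.** The parenthesis could mean 16 mg on any day, and 24 mg at steady state. That reading fits the schedule, since 24 mg is profiled on its first and its last day in most panels and the qualifier would choose between them. It is the less natural reading, and it does not rescue the analysis: the 16-mg day would be undefined and different dosing histories would still be pooled.

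A Panel D participant taken back to 16 mg may stay there (Section 4.1) and would have a Day 13 profile at that dose. That is an unplanned subset selected on tolerability. Section 8.10.6 allows sampling to change, but no change is written, and Part 1 is clinically complete (Section 1.1), so its profiles cannot be moved.

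Three points stand. The pooled schizophrenia bias is much smaller than the worst pairwise figure. The largest shortfalls arise only if Regimen 1 is chosen for Panel E or G. The comparison is exploratory, with no hypothesis, and the 24-mg result is unaffected.

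**Conclusion.** The concern holds. As written, the 16-mg steady-state comparison of AUC0-24hr and Cmax cannot be carried out. This follows from the schedules alone and needs no model.

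If first-day profiles are substituted, the 16-mg ratio carries a dosing-history effect. It runs downward in the healthy comparison, modestly for Panel F and by up to about one Table 4 half-width for Panel G on Regimen 1. In the pooled schizophrenia comparison it is small and of uncertain sign. These sizes rest on linear one-compartment kinetics, a half-life of 8.4 h, assumed absorption shapes and unknown P007 sampling days.

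The defect is confined to the 16-mg AUC and Cmax results. It should be fixed, because a ratio labelled as steady state would be reported and plotted when it is not one.

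**What to change.** In Sections 9.1 and 9.6:

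- (a) Restrict the steady-state AUC0-24hr and Cmax comparison to 24 mg on the last dosing day: Day 13 in D/F; Day 10, 7 or 9 in E/G Regimens 1, 2 and 3; Day 7 in Part 1.
- (b) Keep 16 mg only for C24hr, from the predose sample after the third 16-mg dose (Day 7 in D/F, Day 4 in Panel A and Regimen 1), against P007 at the matching point. Leave out Panel C and Regimen 3, where C24hr after the single 16-mg dose is 0.89–0.92 of steady state. If P007 has no matching sample, drop this comparison too.
- (c) State which P007 day supplies each value.
- (d) Report first-day 16-mg profiles in the descriptive tables, which Section 9.6 already breaks down by dose and day, or compare them only between groups with the same day and preceding dose.

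The cost is SAP wording, with no extra samples. No 16-mg steady-state AUC or Cmax ratio would be reported, but the scheduled samples cannot give one.

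An alternative is to move the profile to the last 16-mg day in panels not yet dosed. Panel A Day 1 profiles must then be excluded from the young 16-mg group, since a last-day profile against Panel A Day 1 gives 1.16–1.54 with no age effect. The Regimen 1 first-dose profile would be lost, and the plan should say so.

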### Number of Participants:

Approximately 100 total participants may be allocated/randomized in Part 1 (n=28, actual sample size as Part 1 is clinically complete) and Part 2 (n ~72). In Part 1, approximately 16 evaluable participants with schizophrenia will complete a generally well-tolerated dose titration.

In Part 2, the intent is to evaluate up to 2 panels of elderly participants with schizophrenia (Panel D and Panel E) and up to 2 panels of healthy elderly participants (Panel F and Panel G).

Up to approximately 16 participants may be enrolled in Panel D and up to approximately 24 participants may be enrolled in Panel E to ensure approximately 16 elderly participants with schizophrenia complete a generally well-tolerated dose titration. Up to approximately 12 participants will be enrolled in Panel F and up to approximately 20 participants will be enrolled in Panel G to ensure approximately 12 healthy elderly participants complete a generally well-tolerated dose titration as described in Section 9.9.

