## 9.9 Sample Size and Power Calculations

Since there are no hypotheses, no power calculations are provided.

Comparison of Elderly vs Young Adults (Exploratory): The between-subject standard deviation estimates for healthy and participants with schizophrenia used in the calculations below were obtained from 24 mg dose in MK-8189 PN007 Panel A and Panel B, respectively. At each of the comparable doses, the precision of the estimates of GMR obtained from the study can be assessed by calculating the half-width of the 90% CIs for the GMRs (elderly/adults) expected for the given sample size and assumed between-subject standard deviation. [Table 4] below shows the half-width of the 90% CI for the true GMR for PK parameters, AUC0-24hr, Cmax, and C24hr.

Table 4 Precision Estimates for AUC0-24hr, Cmax, and C24hr

PK Parameter	Observed (Log) Between-Subject SD	N	(Log) Half-Width of 90% CI	Observed GMR (elderly/adults)	90% CI Based on Observed GMR
elderly with schizophrenia vs adults with schizophrenia					
AUC0-24hr	0.38	12 elderly 12 adults	0.266	1.00	(0.77, 1.31)
Cmax	0.37	12 elderly 12 adults	0.259	1.00	(0.77, 1.30)
C24hr	0.48	12 elderly 12 adults	0.336	1.00	(0.71, 1.40)
healthy elderly vs healthy adults					
AUC0-24hr	0.60	10 elderly 12 adults	0.443	1.00	(0.64, 1.56)
Cmax	0.48	10 elderly 12 adults	0.354	1.00	(0.70, 1.43)
C24hr	1.11	10 elderly 12 adults	0.822	1.00	(0.44, 2.27)
AUC=area under the time-concentration curve from 0 to 24 hours; C24hr=concentration at 24 hours; CI=confidence interval; Cmax=maximum concentration; GMR=geometric mean ratio; N=number; PK = pharmacokinetic, SD = standard deviation ,					

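### The schizophrenia age comparison of PK pools this study's young adults with historical P007 adults without a study term, and no within-study sensitivity analysis is planned

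*Combined protocol and SAP*

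**What the plan says.** Section 9.6 (Comparison of Elderly Participants and Young Adults) makes the schizophrenia comparison "using data from Part 2 (Panels D and E) and Part 1, and historical data from P007 (Panels B and D"). For 16 mg and 24 mg at steady state, log-transformed AUC0-24hr, Cmax and C24hr are fitted with "fixed effects for dose, population (elderly, adult), and population by dose interaction and a random effect for subject". The output is "A two-sided 90% CIs for the true differences in mean for log-transformed AUC0-24hr, Cmax, and C24hr (elderly – adults"), exponentiated to a GMR. The healthy comparison applies the same model to "healthy elderly participants (Panels F and G) to healthy young adults (Panel A in P007").

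Section 9.1 gives the same model. Neither section has a study term, nor an analysis restricted to Part 1 adults. Section 9.1 refers to Section 9.2 for full detail, but Section 9.2 only assigns responsibility for the analyses.

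The comparison is exploratory (Sections 3, 9.3 and 9.9) and there are no hypotheses. The synopsis gives the Part 1 size as "n=28, actual sample size as Part 1 is clinically complete".

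**The concern.** The elderly all belong to one study and the adults to two. The model treats the adults as a single population. The random subject effect cannot absorb a study shift, because each subject belongs to only one study. If exposure at the same dose differed between P007 and this study for reasons such as sites, assay runs or participant mix, part of that difference would be read as an effect of age. The interval would be centred in the wrong place with nothing to show it.

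No hypothesis is tested, so the GMR and its CI are the whole result of this comparison. Section 2.1 says the study is meant to support enrolling elderly participants in later trials, and the age ratio bears on that. Within-study adults already exist: Part 1 is clinically complete, and Section 4.1 has Panel D running alongside it, with Panel E following.

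**Working it through.** **Plan's own figure.** Table 4 takes its SDs from values "obtained from 24 mg dose in MK-8189 PN007 Panel A and Panel B, respectively". For schizophrenia AUC it uses SD 0.38 and "12 elderly 12 adults". Log half-width = t(0.95, 22) × 0.38 × √(1/12 + 1/12) = 1.717 × 0.38 × 0.408 = 0.266, as tabulated. The same formula reproduces the other five half-widths within 0.3%.

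**Adults on active drug.**
- Part 1: 28 randomized. At the 12:4 allocation of Table 2, about 21 are active (assumption; 18 to 24 tried).
- P007 Panel B: 12 active (16 enrolled at 3:1, Section 2.2.2).
- P007 Panel D: 17 active (Section 2.2.2).
- P007 share w = 29/(29 + 21) = 29/50 = 0.58. With 24 or 18 Part 1 actives it is 0.55 or 0.62.

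**Elderly on active drug.** 24 if Panels D and E each supply 12 (Table 2). 18 if Panel D stops at its initial 8 (6 active at 3:1) and Panel E supplies 12.

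**Effect of a study shift on the 24 mg AUC ratio.** Suppose P007 exposure is (1 + d) times that of this study at equal age and dose. The pooled adult log mean moves by w × ln(1 + d), and the GMR is divided by the exponential of that amount. SE = 0.38 × √(1/ne + 1/50), which is 0.104 for ne = 18 and 0.094 for ne = 24. Coverage of the nominal 90% CI comes from the noncentral t distribution with shift bias/SE.

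| P007 exposure (assumed) | Log bias | Factor | GMR shown if truth is 1.00 | Coverage, 24 to 18 elderly |
|---|---|---|---|---|
| 10% higher | 0.58 × 0.0953 = 0.055 | 1.06 | 0.95 | 84-85% |
| 20% higher | 0.58 × 0.1823 = 0.106 | 1.11 | 0.90 | 70-74% |
| 30% higher | 0.58 × 0.2624 = 0.152 | 1.16 | 0.86 | 52-58% |

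Lower P007 exposure moves the ratio the other way, and somewhat further for the same percentage. At 20% lower the factor is 1.14 and coverage is 61-66%.

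**Can the shift be separated?** In the schizophrenia comparison, yes. Adults occur in both studies, and adding a study column to the fixed-effects design gives rank 5 of 5. In the healthy comparison, no. All the elderly are in this study and all the adults in P007, so the rank is 4 of 5.

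**Precision of the within-study contrast (AUC, 24 mg).**
- Pooled, no study term: t × 0.38 × √(1/ne + 1/50) = 0.174 (ne = 18) or 0.157 (ne = 24).
- With a study term: t × 0.38 × √(1/ne + 1/21) = 0.204 or 0.189.

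**Which doses have data?** In Part 1 (Section 1.3.1), 16 mg profiles are taken on Day 1 in Panel A, the first 16 mg dose, and on Day 2 in Panel C, its only 16 mg dose. Panel B never receives 16 mg. Part 1 therefore has no AUC or Cmax profile after repeated 16 mg dosing. At 24 mg every Part 1 panel is profiled on Day 7.

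**The case against.** The other side has a good case, and much of it stands.

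- **The size of the shift is assumed.** A reader might infer that the age ratio is biased. The documents do not support that, because they report no exposure difference between P007 and this study. They show only that the planned analysis could not reveal one.
- **The comparison is exploratory.** No decision rule is tied to the GMR.
- **Pooling can be the better estimator.** A reader might infer that a study term belongs in the main model. With the term, P007 adults add essentially nothing to the 24 mg age contrast. On these inputs pooling has the smaller mean squared error until the log shift exceeds 0.38 × √(1/21 − 1/50)/0.58 = 0.109, or about 11-12% higher exposure in P007. In the 10% scenario pooling wins.
- **Titration history is not a convincing source of difference.** P007's schedules might seem to make its adults unsuitable. But Sections 4.1 and 4.3.1 say the Panel D regimen was used in young adults in P007, while Part 1 adults followed other regimens. With a half-life of about 8.4 hours (Section 2.2.2), three days at a dose is 72/8.4 = 8.6 half-lives, so little history should remain at steady state.
- **The 58% is approximate.** It needs all 29 P007 actives to be evaluable, and Section 2.2.2 reports a withdrawal of consent on MK-8189 in P007 Panel D.
- **Part of the picture is already reported.** Section 9.6 gives geometric means by part and descriptive statistics by part and panel, so an informal check is possible. It does not yield a prespecified GMR with an interval.

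These points limit the finding to a sensitivity analysis at 24 mg. They do not remove the need for one.

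**Conclusion.** The concern holds as a gap in an exploratory analysis. The pooled adult group is about 58% historical, and the model has neither a study term nor a within-study check. A between-study difference would thus pass into the schizophrenia age ratio at about 0.58 of its log size, unseen by the 90% CI. For assumed differences of 10% to 30% higher in P007, the factor is 1.06 to 1.16 and coverage falls from about 85% to as low as 52%. These figures apply to AUC at 24 mg. They rest on SD 0.38, 21 Part 1 actives, all 29 P007 actives evaluable and 18-24 elderly actives.

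In the healthy comparison the whole of any study difference falls on the ratio, and no model term can separate it from age. A reader might expect a covariate such as body weight to help. It cannot break that aliasing, and the documents do not link weight to MK-8189 exposure.

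**What to change.** 1. Keep the pooled model in Section 9.6 as the planned analysis.
2. Prespecify a sensitivity analysis at 24 mg steady state comparing Panels D and E with Part 1 adults only. A fixed study effect at 24 mg is an equivalent route: it rests the age contrast on the same adults. Report both GMRs with their 90% CIs.
3. Label the healthy GMR (Panels F and G against P007 Panel A) as a historical comparison in which study and age cannot be separated.

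The cost is one extra model run on data already planned or collected, plus a sentence of labelling. The sensitivity interval is wider (AUC log half-width about 0.19-0.20 against 0.16-0.17), though still narrower than the 0.266 in Table 4. It does not cover AUC or Cmax at 16 mg, and the plan should say so.
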